8.2 Regimen

N/A – there is no treatment regimen required as part of this study.

8.3 Assignment to Groups

No stratification of subjects will be utilized based on study design.

8.4 Preparation and Handling

The Urodynamic system and air-charged catheters will be prepared, and maintained by the physician.

8.5 Packaging and Labelling

Investigational device labelling will appear on all investigational materials under FDA 21 CFR Subpart 812.5. A copy of the investigational label is shown the Investigator's Brochure.

8.6 Device Accountability

All devices used directly for testing subjects must be recorded using the device LOT number on the subjects CRF form.

8.6.1 *Laborie to Study Site:*

All investigational devices or equipment transferred between Laborie and the study site must be recorded through the Inventory Control Log. This includes postal deliveries and any deliveries made in person by Laborie. Any equipment or devices that are not used and are returned to Laborie must be recorded on the Inventory Control Log as well. It is Laborie's responsibility to ensure that all inventory both at Laborie and the study site correlate. All investigational device accountability will be recorded through the Inventory Control Form.

8.6.2 *Study Site Usage:*

All devices used directly for testing subject samples must be recorded on the Inventory Control Form. All devices used by the study site that are not directly used for the testing of subject samples must be recorded on the Inventory Control Form. This includes any devices used for training or demonstration or any devices which are noted to be defective when opened.

8.6.3 *Study Site to Laborie:*

Any equipment or devices that are not used and are returned to Laborie must be recorded on the Inventory Control Form.

When the devices have been received by Laborie, it is Laborie's responsibility to ensure that all inventory control forms both at Laborie and the study site correlate.

8.7 Concomitant Treatment

Not applicable in this study

8.8 Subject Compliance Monitoring

Not applicable in this study.

9 ASSESSMENT OF INVESTIGATIONAL DEVICE

9.1 Endpoints

OBJECTIVES	ENDPOINTS	JUSTIFICATION FOR ENDPOINTS
Primary		
To confirm the T-DOC® NXT vesical and abdominal catheters are a safe and effective means of measuring UDS pressure in adults.	The primary endpoint will be measured by recording the clinician safety and effectiveness rating for each patient on their CRF. The clinician will indicate whether the T-DOC® NXT vesical and abdominal catheters are safe and effective for measuring UDS pressure in at least 20 of patients enrolled.	Given the intended use of the device, and the fact that there is no single or combination of objective measures generated from the UDS test that can establish the safety and effectiveness, it is justified to obtain clinician feedback via a binary response whether the device was safe and/or effective for measuring UDS pressure.

9.2 Methods of Assessment

A T-DOC® NXT air-charged catheter will be used to assess and record bladder and abdominal pressures which are in turn used by the clinician to identify UDS events. These measurements will be recorded using a LABORIE UDS system. The resulting interpretations regarding safety, effectiveness, and usability will be made by the physician overseeing the subject's case.

All study outcome data captured will be compiled and analysed by the LABORIE study team to determine if the endpoints were successfully achieved based on whether the null hypotheses were accepted or rejected.

10 PATIENT SAFETY

10.1 Definitions

10.1.1 Adverse Events:

Any untoward medical occurrence in a subject, whether or not related to the investigational medical device.

10.1.2 Adverse Device Effect:

Any adverse event related to the use of an investigation medical device.

10.1.3 Device Deficiency:

Inadequacy of a medical device with respect to its identity, quality, durability, reliability, safety or performance

10.1.4 Serious Adverse Event:

An adverse event that:

1. Led to a death;
2. Led to a serious deterioration in health of a patient, user, or others that:
 - a. Results in a life-threatening illness or injury;
 - b. Results in a permanent impairment of a body structure or body function;
 - c. Requires in patient hospitalization or prolongation of existing hospitalization;
 - d. Results in medical or surgical intervention to prevent life-threatening illness or injury or permanent impairment to body structure or a body function;
3. Led to foetal distress, foetal death or a congenital abnormality/birth defect.

10.1.5 Unanticipated Adverse Device Effect:

Any serious adverse effect on health or safety or any life-threatening problem or death caused by, or associated with, a device, if that effect, problem, or death was not previously identified in nature, severity, or degree of incidence in the investigation protocol or application, or any other unanticipated serious problem associated with a device that relates to the rights, safety, or welfare of subjects.

10.1.6 Unanticipated Serious Adverse Device Effect (USADE):

Serious adverse device effect which by nature, incidence, severity or outcome has not been identified in the current version of the risk analysis report.

10.2 Data Collection

Adverse events, device deficiencies, serious adverse events, and unanticipated adverse device effect shall be recorded on the CRF.

10.3 Reporting

All serious adverse events and unanticipated adverse device effects occurring during the investigation will be reported as soon as possible, but no later than 10 working days after the

Investigator/Laborie first learns of the effect. This information will be submitted to Laborie/investigator and the IRB.

10.4 Foreseeable Events

For a complete Risk Management Report please refer to the Risk Management File. The residual risks have been deemed acceptable and the benefits overweighs the risks. Please also refer to Section 4.5 above Assessment of Risks and Adverse Device Effects

10.6 Follow-Up

If an adverse event occurs, any follow-up intervention prescribed is at the discretion of the Investigator, and the site must notify Laborie of the outcome of the follow-up. The study safety endpoint will be measured by capturing adverse event data both during the study visit.

11 STUDY PROCEDURE

11.1 Visit Schedule

Evaluation	Screening & Clinic Visit	
	Part 1*	Part 2
Informed Consent	X	
Inclusion Criteria		X
Exclusion Criteria		X
UDS Study		X
Record any Adverse Events		X
Complete CRF		X

*Part 1 and Part 2 may be combined into 1 visit

11.2 Screening for Eligibility

Subjects may be screened for eligibility for this study by referencing the inclusion criteria. No special testing is required in order to determine eligibility.

11.3 Part 1 (Informed Consent)

1. Conduct Informed Consent discussion with the subject and sign

11.4 Part 2 (Urodynamic Clinic Visit)

1. Determine if the subject is eligible for this study.
2. Conduct Informed Consent discussion with the subject and sign.
3. Collect medical history and record in case report form (TDOC-NXT-01- CRF2).
4. Collect and record other patient details as required on TDOC-NXT-01- CRF1 [weight (lbs), height ('), date of birth, sex, etc].
5. Site personnel will explain what will happen during the UDS test to the subject/parent or caregiver.
6. Site personnel will prepare UDS equipment, study materials, other sterile disposables and supplies as required for the UDS study and record catheter lot number information on TDOC-NXT-01- CRF1.
7. Follow the investigational device instructions for use for placing the catheters. Record all the necessary data on TDOC-NXT-01- CRF1.
8. Conduct UDS study according to ICS Good UDS Practice recommendations, including regular cough checking to ensure good pressure transmission and catheter positioning wherever possible (Rosier *et al.*, 2016). Record all the necessary data on TDOC-NXT-01- CRF1.
9. Site personnel to ask patients to answer questions on urodynamic experience and record all data on TDOC-NXT-01- CRF4.
10. After completing a day of urodynamics, the user is to fill out a questionnaire and record all necessary data on TDOC-NXT-01- CRF3.

NOTE: If an adverse event occurs during this study, any follow-up intervention prescribed is at the discretion of the Investigator. This information should also be recorded on the subject's CRF (TDOC-NXT-01- CRF1-) and the AE form (TDOC-NXT-01- CRF5).

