4.3 Claims and Intended Performance

- The T-DOC® NXT catheter causes minimal discomfort during insertion, during the test, and removal
- Adverse Event Claims as per results
- Subjective claims:
 - The T-DOC® NXT catheters are safe and effective for use on adult patients
 - The T-DOC® NXT catheters are easy to use
 - The T-DOC® NXT catheters are easy to set-up / zero
 - The T-DOC® NXT catheters are easy to insert
 - The T-DOC® NXT catheters have consistent/stable tracings
 - The T-DOC® NXT catheter has adequate subtracted pressures

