4.4 Assessment of Risks and Adverse Device Effects

Risks to the subject will be no greater than those of a standard UDS test. Subjects may experience temporary discomfort upon insertion of the catheters. Test duration may be slightly longer than a standard test while assessment of the study materials is being made, and so discomfort and inconvenience associated with an extended test duration may occur.

UDS testing exposes subjects to risks of urethral instrumentation which can result in infection, urethral trauma and pain (Winters *et al.* 2012). Other risks can include transient discomfort during or following the procedure, transient dysuria or bleeding (hematuria) following the procedure, or urinary tract infection, which occurs in 2-4% of subjects (Chapple, MacDiarmid & Patel, 2009).

In conclusion, the overall residual risks associated with the use of T-DOC® NXT catheters within this study set-up, are acceptable when weighed against the benefits, and are no different than the risks when using other UDS catheter technologies. The sponsor team has also established that patients are subjected to no more than minimal risk since an IDE is not required for this study (Ref: TDOC-NXT-01 - Risk Determination). Lastly, UDS is a widely-performed procedure on subjects requiring specialized management for urinary incontinence/retention problems, as

recommended by the ICS (Abrams *et al.*, 2013), and is useful in characterizing LUT function, identifying causes of symptoms and quantifying related pathophysiological processes (Rosier PF., 2013). Thus, the clinician must weigh the risks and benefits as to whether the UDS test offers additional diagnostic value beyond symptom assessment, physical examination and other diagnostic testing (Winters *et al.*, 2012).

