7 PATIENT SELECTION

7.1 Inclusion Criteria

- Male and Female (Adult age 21+)
- Patients who are scheduled and indicated for UDS testing, for any medically necessary reason as per the physician.

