To evaluate the usability of the device by collecting clinical user feedback and evaluating the following subjective measures using defined ordinal scales: ease of use, ease of insertion, presence of artefacts, stability of the tracing, perceived time savings, ease of voiding around catheter, presence of use errors and overall satisfaction.	The usability performance endpoint will be captured in a questionnaire format. The trained clinical users will rate the T-DOC® NXT performance on a scale of 1-5 on the study outcome questionnaire.
Exploratory Objective 2	
To explore whether the newly designed, smaller sized T-DOC® NXT catheters causes undue discomfort based on subjective subject feedback regarding the discomfort and pain level, for those able to communicate such feedback.	This exploratory endpoint will be measured by collecting patient feedback regarding the level of discomfort and pain experienced during their Urodynamic test using the Numeric Pain Rating Scale (NPRS). Patients capable of providing feedback on a scale, will grade their discomfort/pain at 5 or lower, on the NPRS from 0 ("No Hurt") to 10 ("Hurts worst").

Analysis Populations

All subjects enrolled and completed the urodynamic procedure will be considered in the final analysis. Enrolled subjects who do not undergo the urodynamic procedure or begin the urodynamic procedure but do not complete it (for any reason determined by the investigator to be unrelated to the T-DOC® NXT catheters) will not be included in the final analysis and can be replaced.

If any CRFs are found to be incomplete, the study monitor will follow-up as to the reasoning. If for some reason a clinical user is unable to complete their questionnaire, the questions they have completed will be included in the analysis.

Primary Endpoint

The primary safety and effectiveness endpoint is a binary clinician response after each UDS study using the T-DOC® NXT catheter to determine whether the ability to measure UDS pressure was clinically adequate (success) or inadequate (failure).

In the statistical analysis plan, the null hypotheses for the safety and effectiveness endpoints are designed to rule out success rates $\leq 75\%$.

The allowable Type I error (α) for each hypothesis will be 5% (1-sided), and the Type II error is calculated to be 10% (90% power).

Safety and effectiveness will be evaluated separately via the following sets of hypotheses:

Primary Hypothesis for Safety

H_0 : Safety Success Rate is $\leq 75\%$

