versus

H_A : Safety Success Rate is $> 75\%$

Primary Hypothesis for Effectiveness

H_0 : Effectiveness Success Rate is $\leq 75\%$

versus

H_A : Effectiveness Success Rate is $> 75\%$

The study will be declared a success if both null hypotheses for safety and efficacy are ruled out.

Exploratory Endpoints

Exploratory Objective 1 for Usability Performance

This exploratory endpoint was collected to reflect that the goal of qualitatively describing users' interactions with the device as described in regulatory guidance for usability testing (*FDA's guidance- 'Applying Human Factors and Usability Engineering to Medical Device's, 2016*). A clinical user who completed the T-DOC® NXT clinical study, shall rate the T-DOC® NXT catheter usability performance on a scale of 1-5 for the clinical user questionnaire, comparing their experience with use of their currently used urodynamics catheter on per urodynamic day basis.

Since there will be only daily responses from one user for each of the questions, the results are thus not well-suited to statistical analysis and hypothesis testing is not appropriate. Instead, descriptive statistics will be used to summarize and analyse the results of each question, including: ease of use, ease of insertion, presence of artefacts, presence of coughs/Valsalva response, measurements and tracings of urethral pressure profiles, stability of the tracing, perceived time savings, ease of voiding around catheter, presence of errors and overall satisfaction.

The reported value in the usability performance survey will be analysed using proportions of levels and cumulative proportions of groupings at 95% confidence interval. This includes levels (1 to 5), "Yes and no", "better, same or worse" and any other questions related to usability.

Additionally, the results will be plotted over time to observe the trend as the study continues (preferably a line plot with daily responses over time).

Exploratory Objective 2 for Discomfort/Pain

To satisfy this exploratory endpoint for subject experience, a categorical response variable using the Numeric Pain Rating Scale (NPRS) from 0 ("No Hurt") to 10 ("Hurts worst") will be used. Subjects will grade their discomfort/pain on the scale from 0 ("No Hurt") to 10 ("Hurts worst"). Descriptive statistics will be used to summarize and analyse the results of questionnaires completed per patient for questions about pain during insertion, during test and during removal of the T-DOC® NXT catheters.

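### The discomfort claim is worded causally, but with no pre-insertion score and no comparator the NPRS results only describe discomfort during UDS with this catheter

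*Protocol*

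**What the plan says.** Protocol 4.3 lists the intended claim "The T-DOC® NXT catheter causes minimal discomfort during insertion, during the test, and removal". The SAP's Exploratory Objective 2 uses the same verb: it explores whether the catheter "causes undue discomfort based on subjective subject feedback regarding the discomfort and pain level".

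The data come from Protocol 11.4. Catheter placement is step 7, the UDS study is step 8, and step 9 reads "Site personnel to ask patients to answer questions on urodynamic experience and record all data on TDOC-NXT-01- CRF4". Before placement the steps collect medical history, patient details and catheter lot numbers. Neither those steps, nor the visit schedule in 11.1, nor the SAP mentions a pain or discomfort score before insertion. Protocol 6.1 states that there is no control arm.

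The SAP asks "questions about pain during insertion, during test and during removal of the T-DOC® NXT catheters" on a 0 to 10 NPRS. It reports proportions of score levels and cumulative groupings with 95% confidence intervals. The endpoint text says that patients "will grade their discomfort/pain at 5 or lower, on the NPRS", but it sets no proportion of such scores as success. In the protocol (4.2, 12.2) the objective is exploratory and concerns subjective feedback.

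Patients may enter "for any medically necessary reason as per the physician" (Protocol 7.1). Section 7.2 lists five exclusions, none of them directed at existing pelvic pain as such. Section 4.4 says the test could run a little over a standard one because of study assessments, and that "discomfort and inconvenience associated with an extended test duration may occur".

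**The concern.** A statement that a device causes little or much discomfort needs a reference. With no second arm, the only one available inside the study is the patient's own state just before insertion, and the plan does not describe recording it. People referred for UDS for any indication may arrive with discomfort of their own. A score taken after the test then combines what they arrived with, what the procedure added and what the catheter added.

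At stake is the wording of one claim and one exploratory conclusion. Protocol 19 allows the results to appear in publications or marketing materials, so a causal sentence that the data do not support could reach print.

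**Working it through.** **The plan's own figure.** No figure is given for discomfort. The only sample-size figures (Protocol 12.3) concern the primary endpoints: 81%, 96% and 99% power at 20, 30 and 40 subjects. They reproduce by the exact binomial: take the smallest r whose one-sided 95% Clopper-Pearson lower limit exceeds 75%, then P(X ≥ r) at a true rate of 96%.

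- n = 20: r = 19, power = 20 × 0.96^19 × 0.04 + 0.96^20 = 81.0%
- n = 30: r = 27, power 96.9%
- n = 40: r = 35, power 99.5%

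Nothing below depends on them.

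**What a recorded score contains.** As a simple additive model (my assumption), write R = B + P + C, where R is the recorded score, B is discomfort on arrival, P is what the UDS procedure adds (including any extra test time) and C is what the catheter adds, none of them negative.

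1. R alone gives C ≤ R. A low R therefore limits C, if patients report accurately. A high R says nothing about C.
2. With B recorded, R − B = P + C. Arrival discomfort is removed, but the procedure and the catheter stay together.

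**Illustration (assumed scores).** A patient who arrives at 4 and rises by 2 is recorded as 6, above the SAP's mark of 5. A patient who arrives at 0 and rises by 5 is recorded as 5, within the mark. The raw scores rank the two patients in the opposite order to the rises.

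**Effect of one patient on the reported result.** One patient is 1/20 = 5 percentage points, or 1/40 = 2.5 points. The two-sided 95% Clopper-Pearson lower limits for the proportion scoring 5 or lower are:

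| n | all at 5 or lower | one above 5 | difference |
|---|---|---|---|
| 20 | 0.025^(1/20) = 83.2% | 75.1% | 8.1 points |
| 40 | 0.025^(1/40) = 91.2% | 86.8% | 4.4 points |

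These intervals carry sampling error only. They do not allow for arrival pain, recall or test length.

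**Would a baseline be usable at this size?** The 95% half-width of a mean change is t × SD × √(2(1 − ρ)) / √n. The documents give no SD or correlation, so I assume an SD of 1.5 to 2.5 NPRS points and a before/after correlation ρ of 0.3 to 0.7.

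- n = 20 (t = 2.093): 2.093 × 1.5 × √0.6 / √20 = 0.5, up to 2.093 × 2.5 × √1.4 / √20 = 1.4 points
- n = 40 (t = 2.023): 2.023 × 1.5 × √0.6 / √40 = 0.4, up to 2.023 × 2.5 × √1.4 / √40 = 0.9 points

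That is informative on a 0 to 10 scale.

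**The case against.** The strongest reply is that the protocol's own objective is descriptive and the planned data meet it. No hypothesis is tested, no success rate is set, and the primary endpoints and sample size are untouched. That stands, and it limits the point to an exploratory item.

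Second, the separate insertion, test and removal questions already tie pain to catheter steps. Any extra test time would fall mainly on the during-test item, leaving the other two usable. This also stands, though phase-specific questions do not remove discomfort present on arrival.

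Third, existing pain and a longer test push scores up, against the sponsor's claim, so low scores still favour it. This stands in part. Recall, being asked by site personnel, or reduced sensation could lower scores, so low scores are supportive rather than conclusive.

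Fourth, a baseline score does not separate the catheter from the rest of the procedure, and it does not help with a patient who feels little before or after. This is correct, and it is why the wording must change as well.

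A reader might go further and infer that the study lengthens the test, that all three scores are recalled at the end, or that the discomfort data answer nothing. The documents do not support these readings. The longer test is stated only as a slight possibility. The timing of the questions is inferred from step order: no clock time is given, removal has no step of its own, and the CRFs, where an existing-pain item could sit, were not available for this review.

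**Conclusion.** The point holds for attribution. As described, the NPRS scores report discomfort during UDS with this catheter, by phase. They do not support the causal wording in Protocol 4.3 or SAP Exploratory Objective 2. High scores cannot be assigned to the catheter, and the during-test score may also reflect a slightly longer test. Low scores remain consistent with minimal catheter discomfort.

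The effect on a reported proportion is 5 points per affected patient at 20 subjects and 2.5 at 40. How many patients would be affected cannot be estimated, because the documents give no arrival pain levels. The conclusion assumes that the CRFs contain no pre-insertion pain score beyond what the protocol and SAP describe. It is a cheap improvement to an exploratory objective and does not threaten the study's success criteria.

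**What to change.** 1. In Protocol 11.4, add one NPRS question before catheter insertion, recorded on CRF4.
2. In the SAP, summarise change from that score for insertion, test and removal, alongside the raw proportions already planned.
3. Word the 4.3 claim and the Objective 2 conclusion as discomfort reported during UDS with the T-DOC NXT catheter, rather than discomfort the catheter causes. This is needed even with the baseline score, since the procedure and the catheter remain combined.

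The cost is one extra question per patient, a short SAP addition, the IRB review that Protocol 16 requires for a protocol change, and a slightly narrower claim. No extra staff or procedure is needed. If collection can no longer be changed, the third step can still be taken alone.

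Two further options involve real trade-offs and are not part of this recommendation. Questioning during each phase would interrupt a pressure recording, and resting the claim on insertion and removal alone would give up its during-test part.
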